Table 3-10. Cohort 1, Cohort 2 Groups A and B: Analysis Visit Windows for Posttreatment Hematology, Chemistry, Coagulation, Quantitative Plasma HBV DNA, HBV genotyping, Quantitative HBV Serology (HBsAg, HBcrAg, HBeAg, and HBV RNA), Qualitative HBV Serology (HBeAg, HBeAb, HBsAg, and HBsAb) and Vital Signs

		Visit Window FU Day	
Visit	FU Day	Lower Limit	Upper Limit
FU Week 2*	15	4	22
FU Week 4	29	23	43
FU Week 8	57	44	71
FU Week 12	85	72	127
FU Week 24	169	128	211
FU Week 36	253	212	295
FU Week 48	337	296	≥ 337

^{*} FU Week 2 was defined in protocol amendment 1, but was removed from protocol amendment 2. Since a substantial amount of participants have already completed FU Week 2 per protocol amendment 1, this visit will be kept in analysis.

Table 3-11. Cohort 2 Groups A and B: Analysis Visit Windows for Posttreatment APRI and FibroTest

		Visit Window FU Day	
Visit	FU Day	Lower Limit	Upper Limit
FU Week 12	85	4	211
FU Week 48	337	212	≥ 337

Table 3-12. Cohort 1, Cohort 2 Groups A and B: Analysis Visit Windows for Posttreatment Body Weight, ECG, Estimated Creatinine Clearance (using the Cockcroft-Gault method)

		Visit Window FU Day	
Visit	FU Day	Lower Limit	Upper Limit
FU Week 48	337	4	≥ 337

3.8.3. Selection of Data in the Event of Multiple Records in an Analysis Visit Window

Depending on the statistical analysis method, single values may be required for each analysis window. For example, change from baseline by visit usually requires a single value, whereas a time-to-event analysis would not require 1 value per analysis window.

If multiple valid, nonmissing, continuous measurements exist in an analysis window, records will be chosen based on the following rules if a single value is needed:

- For baseline, the last nonmissing value on or prior to the first dosing date of study drug will be selected, unless specified differently. If multiple measurements occur on the same day, the last nonmissing value prior to the time of first dosing of study drug will be considered as the baseline value. If there are multiple records with the same time or no time recorded on the same day, the baseline value will be the average of these measurements.
- For postbaseline values (except for alanine aminotransferase [ALT]):
 - The record closest to the nominal day for that visit will be selected.
 - If there are 2 records that are equidistant from the nominal day, the later record will be selected.

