 - If there is more than 1 record on the selected day, the average will be taken except for qHBsAg (IU/mL), HBV DNA (IU/mL), and quantitative HBeAg (IU/mL), for which the geometric mean will be taken.

• For postbaseline ALT values:

- The record with the largest value within the same analysis window will be selected.
- If there is more than 1 record with the largest value, the latest record will be selected.
- If there are multiple largest records with the same time or no time recorded on the same day, any one of these measurements can be selected as the analysis value.

If multiple valid, nonmissing, categorical measurements exist in an analysis window, and a single value is needed, records will be chosen based on the following rules:

• For baseline, the last available record on or prior to the date of the first dose of study drug will be selected. If there are multiple records with the same time or no time recorded on the same day, the value with the lowest severity will be selected for safety data (eg, normal will be selected over abnormal for safety electrocardiogram [ECG] findings), and the most conservative value will be selected for efficacy data (eg, negative will be selected over positive for HBeAg and HBsAg, whereas positive will be selected over negative for HBeAb and HBsAb).

• For postbaseline values:

- The most conservative value (eg, abnormal will be selected over normal for safety ECG) within the analysis window will be selected, except for HBV serology (HBsAg, HBsAb, HBeAg, and HBeAb), for which the most favorable value (ie, negative will be selected over positive for HBsAg and HBeAg, whereas positive will be selected over negative for HBsAb and HBeAb) will be selected.
- In the event that more than 1 value within an analysis window are equal, the value collected closest to the nominal day will be selected.
- If there are 2 records that are equidistant from the nominal day, the later record will be selected.
- If there is more than 1 record on the selected day, the latest record will be selected; if these measurements were recorded at the same time or no time recorded, any one of these measurements can be selected as the analysis value.

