4.4.5. Overall Assessment of COVID-19 Pandemic Impact

For participants affected by COVID-19 infection and/or pandemic while participating in the study, a listing of the following individual COVID-19 related outcome categories will be provided:

- Death due to COVID-19
- Adverse event of COVID-19, as determined by COVID-19 SMQ narrow search
- Specific adverse event directly associated with the pathogen causing COVID-19, as determined by MST
- Hospitalization (using data from AE eCRF) due to adverse event of COVID-19 as defined above
- Study drug discontinuation due to COVID-19
- Study discontinuation due to COVID-19
- Missed visits due to COVID-19
- Missed key assessments due to COVID-19 (Key assessments are the assessments contributing to primary endpoint, ie, FU Week 24 assessments related to qualitative HBsAg and quantitative HBV DNA)

In addition, composite broad COVID-19 impact indicator will be derived based on the following individual categories defined above: death, adverse event, hospitalization, study drug discontinuation, study discontinuation, missed visits, and missed key assessments. Composite specific COVID-19 impact indicator will be derived based on death and specific adverse event.

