6. EFFICACY ANALYSES

6.1. Primary Efficacy Endpoint

6.1.1. Definitions of Primary Efficacy Endpoint

The primary efficacy endpoint of this study is defined as the proportion of participants who achieve functional cure, defined as HBsAg loss and HBV DNA < LLOQ at FU Week 24.

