- **HBsAg loss**: HBsAg changing from positive at baseline to negative at any postbaseline visit.
- Confirmed HBsAg loss: HBsAg loss confirmed by any 2 consecutive results.
- HBsAg loss reversion: Any postbaseline HBsAg positive result following HBsAg loss.
- **HBsAb seroconversion**: HBsAb changing from negative or missing at baseline to positive at any postbaseline visit.
- Confirmed HBsAb seroconversion: HBsAb changing from negative or missing at baseline to positive at any postbaseline visit confirmed by any 2 consecutive results.
- **HBsAb** seroreversion: Any postbaseline HBsAb negative result following HBsAb seroconversion.

Both baseline and postbaseline borderline results for HBeAg, HBeAb, HBsAg, and HBsAb will be imputed as follows:

- HBsAb/HBeAb borderline/equivocal → HBsAb/HBeAb negative
- HBsAg/HBeAg borderline/equivocal → HBsAg/HBeAg positive

Missing data will be treated as a nonevent unless otherwise specified (eg, no HBsAg loss, no seroconversion, etc.)

HBeAg-related terminology is defined similarly.

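### For the primary endpoint, qualitative HBsAg is the most favourable result in the FU Week 24 window while HBV DNA is the record nearest Day 169, so discordant repeat samples can only push the functional-cure count up

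*SAP*

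**What the plan says.** SAP Section 6.1.1 sets the primary endpoint as functional cure, "defined as HBsAg loss and HBV DNA < LLOQ at FU Week 24". Section 4.4.5 names the measurements behind it: "FU Week 24 assessments related to qualitative HBsAg and quantitative HBV DNA". One component is thus categorical and the other continuous.

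Both use the same window in Table 3-10, "FU Week 24 169 128 211" (visit, nominal FU day, lower limit, upper limit).

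Section 3.8.3 then treats them differently when a window holds more than one record:

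- **HBV DNA (continuous).** "The record closest to the nominal day for that visit will be selected"; a tie goes to the later record. The same-day rule confirms that HBV DNA belongs here, since it lists "HBV DNA (IU/mL), and quantitative HBeAg (IU/mL), for which the geometric mean will be taken".
- **Categorical results in general.** "The most conservative value (eg, abnormal will be selected over normal for safety ECG) within the analysis window will be selected".
- **HBV serology.** An explicit exception to that default, "for which the most favorable value (ie, negative will be selected over positive for HBsAg and HBeAg".

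Section 6.1 does not require the two components to come from the same visit, and it plans no sensitivity analysis of the selection rule.

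**The concern.** An endpoint assessed at a fixed time should describe the participant's state at about that time. HBV DNA is handled that way. Qualitative HBsAg is not: a single negative anywhere in the window overrides a positive at the scheduled visit. The two components of one composite can then come from different samples, with the HBsAg sample chosen because its result was favourable.

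The choice also runs against the SAP's other conventions. Borderline HBsAg is imputed as positive and missing data count as nonevents (Section 6.2.2). For same-time baseline HBsAg results, negative is preferred and called conservative, since it rules out later loss (Section 3.8.3). Quantitative HBsAg follows the proximity rule, so the qualitative and quantitative HBsAg reported for one visit can come from different samples and disagree.

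At stake is the headline proportion in small groups, where one participant visibly moves the estimate and its interval.

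**Working it through.** **1. Window.** From Table 3-10, the length is 211 − 128 + 1 = 84 days: 169 − 128 = 41 days before the nominal day and 211 − 169 = 42 after. The limits follow the midpoints between adjacent visits with scheduled sampling: (85 + 169)/2 = 127, so the window opens on Day 128, and (169 + 253)/2 = 211.

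**2. Scheduled serology in the window.** Appendix Tables 1 and 2 schedule follow-up HBV DNA and qualitative serology at FU Weeks 4, 12, 24, 36 and 48; FU Week 16 is a virtual visit. The tolerance is ±5 days up to FU Week 16 and ±14 days from FU Week 24. Assuming visits are anchored on the nominal days of Table 3-10:

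| Visit | Allowed FU days | In 128–211? |
|---|---|---|
| FU Week 12 | 85 ± 5 = 80–90 | no |
| FU Week 24 | 169 ± 14 = 155–183 | yes |
| FU Week 36 | 253 ± 14 = 239–267 | no |

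One scheduled sample falls in the window. The selection rule acts only when an unscheduled, repeat, off-schedule or early-discontinuation (ED) sample adds another. Both schedules mark HBV DNA and qualitative serology at the ED visit.

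**3. Applying Section 3.8.3 to constructed participants (values assumed).**

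| Case | Earlier record | Day 169 record | SAP: HBsAg | SAP: HBV DNA | Functional cure under SAP | HBsAg by proximity |
|---|---|---|---|---|---|---|
| A | Day 135: HBsAg negative | HBsAg positive, DNA < LLOQ | negative (Day 135) | < LLOQ (Day 169) | yes | no |
| B | Day 130: HBsAg negative, DNA above LLOQ | HBsAg positive, DNA < LLOQ | negative (Day 130) | < LLOQ (Day 169) | yes | no |

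In case B no single date satisfies both components.

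**4. Direction.** Under the SAP, HBsAg is coded negative if at least one record in the window is negative. Adding a record can turn a positive call negative but never the reverse. HBV DNA selection is the same under either HBsAg rule, so compared with proximity selection the cure count can only stay the same or rise.

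**5. Size.** Planned sizes from Section 1.2 are 40 in Cohort 1, 40 in Cohort 2 Group A and 20 in Group B. One participant is 1/40 = 2.5 points or 1/20 = 5 points. Section 6.1.3 specifies two-sided 95% Clopper-Pearson intervals. For x = 0 the upper limit is 1 − 0.025^(1/n); for x ≥ 1 the limits are the 2.5% quantile of Beta(x, n − x + 1) and the 97.5% quantile of Beta(x + 1, n − x).

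| Count | n = 40 | n = 20 |
|---|---|---|
| 0 | 0% (0 to 8.8) | 0% (0 to 16.8) |
| 1 | 2.5% (0.1 to 13.2) | 5.0% (0.1 to 24.9) |
| 2 | 5.0% (0.6 to 16.9) | 10.0% (1.2 to 31.7) |

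The starting count of zero and the one or two affected participants are assumptions for illustration. Cohort 2 is also reported by HBsAg category, where denominators are smaller and one participant weighs more; the SAP does not give those sizes.

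**The case against.** The strongest reply is that the rule does nothing on scheduled data. It needs a second HBsAg record in the window, discordant results, and HBV DNA below LLOQ on the record nearest Day 169, and the SAP gives a count for none of these. The rule is also prespecified and openly stated, there is no hypothesis test, and Section 6.2.2 summarises confirmed HBsAg loss separately. All of that stands and limits how often the problem can arise. It does not make the rule suitable for the primary endpoint, because those summaries do not alter the primary proportion.

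A reader might also infer more than the SAP supports:

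- **That HBsAg or HBsAb reversion is hidden.** Section 6.2.2 defines reversion on any postbaseline result after loss or seroconversion, and Section 3.8.3 picks one value only where a single value is needed. Nothing says reversion is derived from window-selected values.
- **That extra draws cluster in participants with rebound or flare.** The SAP does not say so. A participant whose selected HBV DNA is at or above LLOQ fails the composite whichever HBsAg value is chosen.
- **That the 84-day window is itself a fault beside the ±14-day tolerance.** It follows from using midpoints between visits.
- **That the two components are typically far apart.** An 83-day gap (211 − 128) is attainable with paired records on Days 128 and 211: HBV DNA comes from Day 128 (41 days off against 42) and the negative HBsAg from Day 211. That is late loss, not reversion. With a scheduled visit in tolerance and HBV DNA drawn, the largest gap is 211 − 155 = 56 days.
- **That defining HBsAg loss as "HBsAg changing from positive at baseline to negative at any postbaseline visit" lets any negative count.** That wording belongs to the secondary-endpoint section; Section 6.1.1 ties the primary endpoint to FU Week 24.

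**Conclusion.** The point holds as a conditional one. Where a participant has discordant HBsAg results in the FU Week 24 window, the SAP as written can count as a functional cure someone who was HBsAg-positive at the scheduled visit, and nothing in Section 6.1 prevents it. Any resulting error in the primary proportion is upward, by 2.5 points per participant at n = 40 and 5 points at n = 20. The conclusion rests on Section 4.4.5 identifying qualitative HBsAg as the primary-endpoint input, on the planned group sizes, and on visits anchored to the nominal days of Table 3-10.

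It would go too far to say that the primary proportion is biased upward as a matter of fact. If no participant has discordant records in the window, the rule changes nothing. The rule still merits correction, because the error can run in only one direction and the remedy is already in the same section of the SAP.

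**What to change.** For the primary endpoint, state that qualitative HBsAg is selected by the rule used for HBV DNA: the record nearest the nominal FU day, with a tie going to the later record. For discordant results on the selected day, take positive over negative. Both components will then normally come from the same visit.

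A strict same-date requirement is not needed. It could make a participant a nonresponder because one assay was missing that day, even with a valid result nearby.

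Keep the most-favourable selection at most as a labelled sensitivity analysis. Participants who were ever HBsAg-negative already have their own summary in Section 6.2.2, so nothing is lost.

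The cost is a wording change and a small derivation change. Section 1 provides for changes after SAP finalization to be documented in the CSR. The reported proportion may be slightly lower.

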4. PARTICIPANT DISPOSITION

4.1. Participant Enrollment and Disposition

Key study dates (ie, first participant screened, first participant enrolled, last participant last visit for the primary endpoint, and last participant last visit for the clinical study report) will be provided.

A summary of participant enrollment will be provided by cohort for each country or region, investigator within a country or region, and study overall. Within Cohort 2, the summary will be presented by treatment group (Group A or Group B) and stratification group (HBsAg \geq 3 or HBsAg \leq 3 log₁₀ IU/mL). The summary will present the number and percentage of participants enrolled/randomized. For each column, the denominator for the percentage calculation will be the total number of participants analyzed for that column. For Cohort 2, if there are discrepancies in the value used for stratification assignment between the IXRS and the clinical database, the value collected in the clinical database will be used for the summary. A listing of participants with discrepancies in the value used for stratification assignment between the IXRS and the clinical database at the time of data finalization will be provided.

The randomization schedule used for Cohort 2 will be provided as an appendix to the CSR.

A summary of participant disposition will be provided by cohort and study overall. Within Cohort 2, the summary will be presented by treatment group (Group A or Group B) and stratification group (HBsAg \geq 3 or HBsAg \leq 3 log₁₀ IU/mL). This summary will present the number of participants screened, the number of participants who met all eligibility criteria but were not enrolled/randomized with reasons participants not enrolled/randomized, and the number of participants in each of the categories listed below:

- All Enrolled Analysis Set
- All Randomized Analysis Set
- Full Analysis Set
- Safety Analysis Set
- FU Analysis Set
- SLGN PK Analysis Set
- SLGN PK Substudy Analysis Set
- SLGN completion status
 - Completed SLGN
 - Prematurely discontinued SLGN

- Reasons for premature discontinuation of SLGN
- Nivolumab completion status
 - Nivolumab not initiated
 - Completed nivolumab
 - Prematurely discontinued nivolumab
- Reasons for premature discontinuation of nivolumab
- VIR-2218 completion status
 - Completed VIR-2218
 - Prematurely discontinued VIR-2218
- Reasons for premature discontinuation of VIR-2218
- TAF completion status (for Cohort 1 during treatment phase only)
 - Completed TAF
 - Prematurely discontinued TAF
- Reasons for premature discontinuation of TAF
- FU Completion Status
 - Continuing FU (for FU Week 24 Analysis)
 - Completed FU
 - Prematurely discontinued FU
- Study completion status
 - Continuing study (for FU Week 24 Analysis)
 - Completed study
 - Premature discontinued study
- Reasons for premature discontinuation of study

For the status of study drugs, FU completion, and study completion and reasons for premature discontinuation, the number and percentage of participants in each category will be provided. The denominator for the percentage calculation will be the total number of participants in the Safety Analysis Set corresponding to that column. In addition, a flowchart will be provided to depict the disposition.

The following by-participant listings will be provided by cohort (and by treatment group for Cohort 2), and participant identification (ID) number in ascending order to support the above summary tables:

- Reasons for premature study drug or study discontinuation
- Lot number and kit ID

4.2. Extent of Study Drug Exposure and Adherence

Extent of exposure to study drug will be examined by assessing the total duration of exposure to study drug and the level of adherence relative to the study drug regimen specified in the protocol.

4.2.1. **Duration of Exposure to Study Drug**

Total duration of exposure to a study drug during treatment period will be defined as follows:

- Duration of exposure to TAF = last dosing date of TAF for the treatment period first dosing date of TAF for the treatment period + 1 day
- Duration of exposure to SLGN = last dosing date of SLGN first dosing date of SLGN + 7 days
- Duration of exposure to VIR-2218 = last injection date of VIR-2218 first injection date of VIR-2218 + 28 days
- Duration of exposure to nivolumab = last injection date of nivolumab first injection date of nivolumab + 28 days

The calculations for duration of exposure to study drugs are made regardless of any temporary interruptions in study drug administration and will be expressed in weeks using up to 1 decimal place (e.g., 4.5 weeks). If the last study drug dosing date is missing, the latest date among the study drug end date, clinical visit date, laboratory sample collection date, and vital signs assessment date that occurred during the on-treatment period will be used for participants included in the Final Analyses or the last available date in the database snapshot for FU Week 24 Analysis. If month and year of the last dose are known, and the last study drug dosing date imputed above is different from the month collected, the last date of that month will be used. If only year of the last dose is known, and the last study drug dosing date imputed above is after the year collected, the last date of that year will be used; if the last study drug dosing date imputed above is before the year collected, the first date of that year will be used.

The total duration of exposure to each of the study drugs will be summarized using descriptive statistics and using the number (ie, cumulative duration of exposure by weeks) and percentage of participants exposed through the following time periods: 1 day, 4 weeks, 8 weeks, 12 weeks, 16 weeks, 20 weeks, 24 weeks, 28 weeks, 32 weeks, and 36 weeks, where applicable. Summaries will be drug specific and be provided by cohort (and by treatment group for Cohort 2) for the Safety Analysis Set.

For nivolumab, number of doses administered (ie, 6 doses, 5 doses, 4 doses, 3 doses, 2 doses, and 1 dose) will be summarized by cohort (and by treatment group for Cohort 2) for the Safety Analysis Set.

No formal statistical testing is planned.

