1.2. Study Design

Approximately 40 NUC-suppressed and 60 viremic CHB-infected participants may be enrolled and assigned into a cohort below. Each cohort will enroll a minimum of 20% of HBeAg-positive participants, and up to 20% of participants can have HBsAg \leq 100 IU/mL.

NUC-suppressed Cohort

Cohort 1 (n = 40):

- TAF 25-mg tablet administered orally once daily for 36 weeks
- VIR-2218 200 mg administered via SC injection once every 4 weeks for 24 weeks (total 6 doses)

At Week 12, add-on and initiate the below treatment:

- SLGN 3 mg (2 × 1.5-mg tablets) administered orally while fasting once a week on the same day for 24 weeks (total 24 doses)
- Nivolumab 0.3 mg/kg administered IV once every 4 weeks for up to 24 weeks (up to 6 doses)

Viremic Cohort

Cohort 2 (n = 60)

Participants will be randomized 2:1 into Cohort 2 (Groups A and B) and stratified by HBsAg > or \leq 3 log₁₀ IU/mL.

Group A (n = 40):

• VIR-2218 200 mg administered via SC injection once every 4 weeks for 24 weeks (total 6 doses)

At Week 12, add-on and initiate the below treatment:

- SLGN 3 mg (2 × 1.5-mg tablets) administered orally while fasting once a week on the same day for 24 weeks (total 24 doses)
- Nivolumab 0.3 mg/kg administered IV once every 4 weeks for up to 24 weeks (up to 6 doses)

[figure not shown]
Group B (n = 20):

- SLGN 3 mg (2×1.5 -mg tablets) administered orally while fasting once a week on the same day for up to 24 weeks (up to 24 doses)
- Nivolumab 0.3 mg/kg administered IV once every 4 weeks for up to 24 weeks (up to 6 doses)

After completing study treatments all participants will enter the FU period.

Figure 1-1 provides the study design schema.

Figure 1-1. Study Design Schema*

IV = intravenous; NUC = nucleos(t)ide(s); PO = oral; Q4W = every 4 weeks; QD = once daily; QW = every week; SLGN = selgantolimod; SC = subcutaneous; TAF = tenofovir alafenamide

- a Viremic participants who meet criteria to initiate NUC treatment will receive TAF 25 mg once daily for up to 36 weeks during the study.
- b SLGN dosed while fasting once a week, on the same day, for 24 weeks.
- c Participants will continue to receive TAF per Protocol Section 3.5.
- * NOTE: Nivolumab dosing was stopped in this study and all treatments in Cohort 2 Group B were discontinued. This was a sponsor decision based on a benefit risk assessment on the use of nivolumab in HBV cure. Rationale is provided in Protocol Section 1.3.1.

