1.3. Sample Size and Power

2. TYPE OF PLANNED ANALYSIS

2.1. Primary Analysis

The Primary Analysis will be conducted after all participants have completed FU Week 24 or early terminated from the study prior to FU Week 24.

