3.6. Missing Data and Outliers

3.6.1. Missing Data

In general, missing data will not be imputed unless methods for handling missing data are specified. Exceptions are presented in this document.

For missing last dosing date of study drug, imputation rules are described in Section 4.2. The handling of missing or incomplete dates for AE onset is described in Section 7.1.6.4, and for prior HBV and concomitant medications in Section 7.4.

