3.8.2. Analysis Visit Windows

Participant visits might not occur on protocol-specified days. Therefore, for the purpose of analysis, observations will be assigned to analysis windows as specified in Table 3-1 to Table 3-12.

Data collected up to the last on-treatment date + 3 days will be considered as on-treatment data, whereas data collected afterwards will be considered as follow-up data.

For each drug, the last on-treatment date is defined as follows:

- Last on-treatment date for VIR-2218 = (last injection date of VIR-2218 + 28 days) -1
- Last on-treatment date for nivolumab = (last injection date of nivolumab + 28 days) 1
- Last on-treatment date for selgantolimod = (last dose date of selgantolimod + 7 days) -1

For Cohort 1 and Cohort 2 Group A, the composite last on-treatment date is the latest date of the last on-treatment date of VIR-2218, nivolumab, or SLGN.

For Cohort 2 Group B, the composite last on-treatment date is the latest date of the last on-treatment date of nivolumab or SLGN.

Participants are allowed to continue taking TAF after the discontinuation of study treatments, hence TAF will not be considered for constructing the analysis windows.

The follow-up day (FU Day) in Posttreatment tables is defined as:

• FU Day = Assessment date – composite last on-treatment date.

A baseline value is defined as the last available value collected on or prior to the date of first dose of any study drug. An unscheduled visit prior to the first dosing of study drug will be included in the calculation of the baseline value, if applicable.

The analysis windows for on-treatment assessments are provided in Table 3-1 to Table 3-9. Table 3-10 to Table 3-12 provide analysis windows for posttreatment assessments.

Table 3-1. Cohort 1 and Cohort 2 Group A: Analysis Visit Windows for On-treatment Vital Signs, Hematology, Chemistry, Coagulation, Quantitative Plasma HBV DNA, Quantitative HBV (serum HBsAg, HBcrAg, HBeAg, and HBV RNA), Qualitative HBV Serology (HBeAg, hepatitis B e antibody (HBeAb), HBsAg, and hepatitis B surface antibody (HBsAb))

		Visit Window Study Day	
Visit	Study Day	Lower Limit	Upper Limit
Baseline	1	(none)	1
Week 4	29	2	43
Week 8	57	44	71
Week 12	85	72	92
Week 14	99	93	106
Week 16	113	107	127
Week 20	141	128	155
Week 24	169	156	183
Week 28	197	184	211
Week 32	225	212	239
Week 36	253	240	≥ 253

Table 3-2. Cohort 1 and Cohort 2 Group A: Analysis Visit Windows for On-treatment Urinalysis

		Visit Windo	w Study Day

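### For a wholly missing last dosing date, the FU Week 24 Analysis imputes the last snapshot date with no on-treatment limit, in conflict with the Final Analysis rule in the same sentence

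*SAP*

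**What the plan says.** SAP Section 4.2.1 covers a missing last dosing date in one sentence with two branches. In the first, the latest of four kinds of date (drug end, visit, laboratory sample, vital signs) "that occurred during the on-treatment period will be used for participants included in the Final Analyses". The second branch is "or the last available date in the database snapshot for FU Week 24 Analysis", with no on-treatment limit. If the month and year are known and the imputed date falls in another month, the last day of the known month is used. A known year alone limits the date only to within that year.

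Section 2.1 places the FU Week 24 (Primary) Analysis "after all participants have completed FU Week 24 or early terminated from the study prior to FU Week 24". Section 3.6.1 points to the same rule in general terms: "For missing last dosing date of study drug, imputation rules are described in Section 4.2".

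Section 3.8.2 builds the last on-treatment date of each drug from its last dose, and a composite date from the latest of these. It then states: "Data collected up to the last on-treatment date + 3 days will be considered as on-treatment data". Treatment-emergent adverse events (Section 7.1.6.1) and laboratory abnormalities (Section 7.2.2.1) run to the composite date plus 30 days. TAF is not used for the windows.

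**The concern.** A snapshot date is a sensible stand-in for participants still being dosed at a data cut. At this cut nobody is still receiving SLGN, VIR-2218 or nivolumab. Section 4.1 agrees: it has a continuing category at the FU Week 24 Analysis for follow-up and for the study, but none for any study drug. Section 4.2.1 tabulates exposure only to 36 weeks.

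For someone who reached FU Week 24, the snapshot date therefore lies about 24 weeks or more after treatment ended. Exposure is overstated, and the same participant gets a different value in the Final Analysis under the same SAP. If the imputed date also feeds Section 3.8.2, follow-up data are relabelled as on-treatment, which affects visit windows, treatment-emergent status and possibly the FU Week 24 record behind the primary endpoint.

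**Working it through.** **Inputs.** Sections 1.2 and 3.8.2: in Cohort 1 and Cohort 2 Group A, SLGN is weekly from Week 12 (Day 85), 24 doses; VIR-2218 is every 4 weeks from Day 1, 6 doses; nivolumab is every 4 weeks from Week 12, up to 6 doses; Cohort 1 TAF is daily for 36 weeks. Section 4.2.1: exposure is last minus first dosing date, plus 7 days (SLGN), 28 days (VIR-2218, nivolumab) or 1 day (TAF). Table 3-10 gives the nominal FU day and its limits: "FU Week 24 169 128 211".

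**Step 1: reproduce the planned durations (nominal completer).**
- SLGN: last dose Day 85 + 23×7 = 246; (246 − 85 + 7)/7 = 24.0 weeks.
- VIR-2218: last dose Day 1 + 5×28 = 141; (141 − 1 + 28)/7 = 24.0 weeks.
- Nivolumab, six doses: last dose Day 85 + 5×28 = 225; (225 − 85 + 28)/7 = 24.0 weeks.
- TAF: 252/7 = 36.0 weeks.
- Composite last on-treatment date: the latest of 246 + 6 = 252, 141 + 27 = 168 and 225 + 27 = 252, so Day 252.

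The SAP's planned durations are reproduced.

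**Step 2: apply the FU Week 24 rule to a wholly missing date.** Assumption: the participant's last date in the snapshot is the FU Week 24 visit at FU Day 169, which is Day 252 + 169 = 421.

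| Drug | Nominal weeks | Imputed weeks | Ratio |
|---|---|---|---|
| SLGN | 24.0 | (421 − 85 + 7)/7 = 49.0 | 2.04 |
| VIR-2218 | 24.0 | (421 − 1 + 28)/7 = 64.0 | 2.67 |
| Nivolumab, six doses | 24.0 | (421 − 85 + 28)/7 = 52.0 | 2.17 |
| TAF (treatment period) | 36.0 | 421/7 = 60.1 | 1.67 |

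Over the FU Day 128 to 211 window, SLGN runs from 43.1 to 55.0 weeks (1.80 to 2.29 times nominal). A Group B participant who stopped SLGN after 12 doses goes from 12.0 to 37.0 weeks.

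**Step 3: consequences if the imputed SLGN date enters Section 3.8.2.**
- Composite date: 421 + 6 = Day 427, instead of Day 252.
- On-treatment data run through 427 + 3 = Day 430.
- The FU Week 24 visit has FU Day 421 − 427 = −6. It falls in the Week 36 window of Table 3-1, which is open-ended above Day 253.
- Treatment-emergent cutoff: 427 + 30 = Day 457, instead of 252 + 30 = Day 282.

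**Step 4: the Final Analysis rule for comparison.** With the latest eligible date at the composite date plus 3 days (Day 255), SLGN is (255 − 85 + 7)/7 = 25.3 weeks, six-dose nivolumab 28.3 and TAF 36.4. VIR-2218 is still (255 − 1 + 28)/7 = 40.3 weeks, because SLGN sets the composite period. This rule is also circular: the on-treatment period that limits the imputed date is itself derived from the missing last dose.

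**Step 5: effect on a group summary.** One affected participant in 40 moves mean SLGN exposure from 24.0 to (39×24 + 49)/40 = 24.6 weeks.

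**The case against.** The trigger is narrow. Section 3.8.1 takes the last dose date from the eCRF stop date on the permanent-withdrawal record. VIR-2218 and nivolumab have injection dates, so the realistic case is weekly oral SLGN. A known month and year holds the error to within that month. The SAP gives no count of missing dates, and it may be zero. All of this stands; it limits how often the rule acts, not what the rule does when it acts.

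Three stronger readings are tempting and are not supported:

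- *Everyone has been off all treatment for about 24 weeks, and exposure doubles.* Section 2.1 also admits early terminators, who may have less follow-up. TAF may continue in follow-up and does not move the windows. A factor near two fits SLGN and six-dose nivolumab, but not TAF (1.67) or VIR-2218 (2.67).
- *The SAP certainly relabels follow-up data.* Section 3.8.2 does not itself invoke the imputation. The link runs through Section 3.6.1, which is worded generally but only points to Section 4.2. Applying it there is the natural reading, but it is not stated.
- *The affected participant is scored as a primary-endpoint failure.* The nonevent rule for missing data stands in Section 6.2.2, under the secondary endpoints. Section 6.1 does not adopt it. Even if it is carried over, the estimate changes only if that participant was a true responder: at most 1/40 = 2.5 points, or 1/20 = 5 points in Group B.

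One could also argue that the on-treatment limit was meant for both branches. The sentence attaches it only to the first.

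**Conclusion.** The point holds as a conflict between two stated rules, one of which gives a wrong result when followed as written. In a completer with a wholly missing date, SLGN exposure would be reported as 49.0 weeks in the FU Week 24 Analysis and at most about 25.3 weeks in the Final Analysis, against a nominal 24.0. These figures assume nominal dosing days and a last snapshot date at FU Day 169; a later snapshot date makes the gap larger.

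The shift of the composite date from Day 252 to Day 427, with follow-up adverse events and laboratory abnormalities becoming treatment-emergent, depends on Section 3.6.1 carrying the rule into Section 3.8.2. The primary-endpoint effect depends further on the nonevent rule being applied and on the participant being a responder. With an unknown and possibly zero number affected, this is a defect of logic that is cheap to repair, not a demonstrated bias in the results.

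**What to change.** Delete the snapshot-date clause from Section 4.2.1. Use one on-treatment-limited rule in both analyses, applied per drug and anchored to data other than the missing date:

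- **VIR-2218 and nivolumab:** the last recorded administration date.
- **SLGN and treatment-period TAF:** the latest recorded dosing, dispensing, return or visit date up to the scheduled EOT visit, or up to the treatment discontinuation date if that is earlier.

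State in Section 3.8.2 whether the imputed date is used for the composite last on-treatment date.

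Two shortcuts should be avoided. First, do not cap SLGN at its last dispensing visit. In Cohort 1 and Group A that is Week 32 (Day 225), which gives (225 − 85 + 7)/7 = 21.0 weeks for a completer and a last on-treatment date of Day 231. Unless a later nivolumab date holds the composite date, the EOT visit on Day 253 then becomes FU Day 22 and falls in the FU Week 2 window. Second, do not use an ED visit as the limit when it occurs in follow-up, which Appendix Table 1 allows.

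The cost is one deleted clause and a short replacement rule, with no new data collection. Section 1 provides for changes after SAP finalization to be documented in the CSR.
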